### Preliminary Results and Demonstration of Plausibility

To calculate the test retest reliability, we obtained two PBR28 scans (107), on average 1.4 weeks apart, on 4 clinically stable relapsing-remitting MS subjects (age  $41 \pm 7$  years, two men/two women) and four healthy control (age  $42 \pm 8$  years, 2 two men/two women), matched for translocator protein genotype for test. Mean test VT values ( $ml cm^{-3}$ ) were  $3.9 \pm 1.4$  in the whole brain gray matter (GM),  $3.6 \pm 1.2$  in the whole brain white matter (WM) or normal-appearing white matter (NAWM), and  $3.3 \pm 0.6$  in MS WM lesions; mean retest VT values were  $3.7 \pm 1.0$  in GM,  $3.3 \pm 0.9$  in WM/NAWM, and  $3.3 \pm 0.7$  in MS lesions. Test-retest results showed a mean absolute TRV ranging from 7 to 9 % across GM, WM/NAWM, and MS lesions. Another MS subject (age 41 years, male) with clinical and radiological activity was studied for lesion detectability.

[figure not shown]

Figure 1 – The top row contains three slices of a gadolinium enhanced T1, showing a white matter lesion in the right mesial frontal subcortex. The bottom row shows the same three sections with PBR28 spatially corresponding to the exacerbating lesion. (Figure-1).

We thus showed that PBR28 scanning has good test-retest reproducibility in humans and can localize focal inflammation. To show its utility in imaging more diffuse inflammation, we employed the primate endotoxemia model (108). Six female baboons (*Papio anubis*) were scanned before and at 1h and/or 4h and/or 22 h after intravenous administration of *E. coli* lipopolysaccharide (LPS; 0.1mg/kg), which induces systemic inflammation (figure 2). LPS administration increased [(11)C]PBR28 binding ( $F(3,6)=5.1$ ,  $p=.043$ ) with a  $29 \pm 16\%$  increase at 1h ( $n=4$ ) and a 62

[figure not shown]

Figure 2 – A representative baboon brain. A) MRI of brain. B) This is the baseline image showing sparse inflammation. C) Increased inflammation 1 hour post injection of LPS. D) It reaches a maximum 4 hours post injection.

$\pm 34\%$  increase at 4h (n=3) post-LPS106. Significantly immunohistochemistry from one baboon showed immunoreactivity exclusively in microglia and not in astrocytes.

Next we applied the same paradigm to healthy young volunteers using a reduced dose of LPS (1ng/kg). We recruited eight (109) healthy non-smoking consented males (24.9 $\pm$ 5.5 years old, 87.5 $\pm$ 12.3 kg) and imaged them pre and post LPS administration. Eight healthy male subjects each had two 120-min [(11)C]PBR28 PET scans in 1 d, before and after an LPS challenge. LPS (1.0 ng/kg, i.v) was administered 180 min before the second [(11)C]PBR28 scan. LPS administration significantly increased [(11)C]PBR28 binding 30-60%, demonstrating microglial activation throughout the brain (Figure 3). This increase was accompanied by an increase in blood levels of inflammatory cytokines, vital sign changes, and sickness symptoms, well-established consequences of LPS administration. To our knowledge, this was the first demonstration in humans that a systemic LPS challenge induces robust increases in microglial activation in the brain.

[figure not shown]

Figure 3A- Average VT images with the magnetic resonance image (MRI) shown for anatomical reference (Top row). Significance level was  $*P < 0.01$  (linear mixed models) of the difference between baseline and post-LPS challenge scans.

between patients with Alzheimer's disease and normal controls.

Figure 3A demonstrates the changes in mean PBR28 binding of 8 healthy subjects. There is heterogeneity in the increases in the absolute values of the increases in binding Figure 3A- Average VT images with the magnetic resonance image (MRI) shown for anatomical reference (Top row). Significance level was  $*P < 0.01$  (linear mixed models) of the difference between baseline and post-LPS challenge scans. after the administration of LPS in this young healthy cohort perhaps reflecting variability in microglial reactivity reserve. It is also notable in Figure 3B that regional microglial reactivity reserve indices vary from the lowest in the thalamus to the highest in the parietal lobes. This ties in well with the NIMH study showing the greatest difference in the level of baseline activation can be found by comparing parietal lobes

[figure not shown]

Figure 3B- LPS administration significantly increases [11C]PBR28 binding (VT) from baseline in healthy control subjects (n = 8) shown in A, regional percent increase in VT averaged across subjects (error bars are SEM). (B) VT for each subject averaged across regions examined in high-affinity (squares) and mixed-affinity binders (circles).

The magnitude of the post LPS signal prompted us to think of the human endotoxemia paradigm as a physiological test of the innate immune system, especially microglial activation in response to molecular pattern associated with PAMPs and DAMPs (see significance). The microglia activation reserve index would be defined by the proportional increase in the baseline level of PBR28 binding in response to LPS.

**3. Research Plan:** Summarize the study design and research procedures using non-technical language that can be readily understood by someone outside the discipline. **Be sure to distinguish between standard of care vs. research procedures when applicable, and include any flowcharts of visits specifying their individual times and lengths.** Describe the setting in which the research will take place.

**Aim-** To examine the differences in the capacity to activate microglia in patients with AD compared to age-comparable cognitively normal subjects and younger healthy controls.

**Hypothesis:** *In early AD the innate immune response becomes more reactive to PAMPs and DAMPs compared to those with normal cognition.*

#### Rationale

Amyloid deposition plateaus before the onset of symptoms. As such MCI resembles AD more than cognitively normal subjects in terms of amyloid status. Yet the NIMH study showed a significant difference in microglial activation in AD and

not MCI or cognitively normal subjects. One possible explanation may be increased reactivity of microglia to ambient amyloid in AD. If true, this may be the mechanism that drives disease progression after amyloid deposition has plateaued. The use of PBR28 in patients with Alzheimer's disease presents significant advantages over the previous modes of study of neuroinflammation *in vivo*. Using this ligand, we aim to demonstrate dysregulation of the immune system in early AD compared to normal aging.

**Presently amyloid specific therapies are the only avenue sought for treatment of Alzheimer's disease. The study has the potential to revolutionize our approach to therapy.**

### Procedure

#### Screening and selection procedures:

*Screen/Baseline visit to ADRU:* Each subject will have an initial screening visit that will include:

Screening: Demographics, history, examination, GDS, EKG, Labs, MOCA, logical memory I/II, CDR and Informed consent. Baseline: WAISIII – picture completion, digit symbol, symbol search, arithmetic, digit span, information, letter number sequencing, RAVLT, Trails A/B, Boston naming, Stroop, FAS, Rey complex figure, ADCS-ADL, CAM and NPI. In certain cases, this can take more than 4 hours and we may need to split the day into two where screening and baseline are administered on separate days.

*Possible pre-imaging visit to MRRC:* Many of the patients who will enroll will already have clinical MRI. For those who do not we will organize one for this research.

#### *Imaging visit to PET center:*

On the day of the scan there are two steps performed:

Step 1:

1. arterial line placement (there is no suitable reference region)
2. 1st scan – 120-min emission

Step2:

3. LPS injection 3 hours prior to 2nd scan, fasting for 8 h prior to this injection
4. 2nd scan – 120-min emission
5. Optional blood draw during the PET center visit If the participant agrees, 10-20mls of blood will be taken at 0,1,3 and 6 hours and banked at [name] in [name] Laboratory. These samples will only be stored in [name] laboratory; they will not be added to one of [name] existing repositories. The samples will be used by only the investigators on this project; they will not be made available to outside researchers.

In certain cases, the length of this day may not be tolerated by the subject on the day so that we divide the day into two where Steps 1 and 2 are administered on separate days.

Note: White coat hypertension is a common phenomenon in the elderly population. During the visit to the PET center, the unfamiliarity of the environment, the placement of the arterial line, and other cannulae can have an additive effect to the white coat phenomenon. Subject's will be asked to bring any prescribed hypertension medication to the scanning day. High blood pressure does not predictably increase the risk during endotoxin administration as the latter often reduces blood pressure. Furthermore, patients with unstable hypertension will be excluded from the protocol. However, in the interest of patient safety and ethical consideration of ignoring a possibly significant clinical finding, [name] will implement the following protocol:

1) If blood pressure is raised (SBP > 180 or DBP > 100) and patient is symptomatic:

- a) If the symptoms raise concerns of end organ damage (chest pain, SOB, focal neurological sign, thunderclap headache, etc) the patient will be referred to the ED via ambulance.
- b) If headache is the only symptom and the headache is more severe or different character than the patients habitual headaches, then the experiment will be stopped. The patient's primary care physician will be contacted or the patient will be referred to urgent care.

2) If blood pressure is raised (SBP > 180 or DBP > 100) and patient is asymptomatic (except for regular headaches):

- A) If the patient has their hypertension medication as instructed, if not otherwise indicated, the patient will be given an extra dose of their prescribed hypertension medication. Their BP will be retaken before administration of the endotoxin. If their BP is still >180/100 or if the patient is hypotensive, the

administration of the endotoxin will be delayed or cancelled. If the BP is optimal, we will proceed with endotoxin administration.

- B) If the patient is prescribed hypertension medication but did not bring it to the scanning day, [name] will order one dose of the prescribed medication unless there is a contraindication. The medication will be ordered through EPIC, sent to the CVS at [name], and picked up by the patient's scan day companion. The cost of the study medication will be covered by the study. Their BP will be retaken before administration of the endotoxin. If their BP is still >180/100 or if the patient is hypotensive, the administration of the endotoxin will be delayed or cancelled. If the BP is optimal, we will proceed with endotoxin administration.
- C) If the patient is not prescribed hypertension medication, [name] will order amlodipine through EPIC. The medication will be sent to the pharmacy and picked up by the patient's scan day companion. The medication will be given in 2.5mg or 5mg doses at 30 minute intervals. If the patient permits, this intervention will be communicated with their PCP. The medication will be provided at no cost to the patient. Their BP will be retaken before administration of the endotoxin. If their BP is still >180/100 or if the patient is hypotensive, the administration of the endotoxin will be delayed or cancelled. If the BP is optimal, we will proceed with endotoxin administration.

If a subject becomes hypotensive after the administration of anti-hypertensive medication, [name] will implement the following protocol.

- A) If the subject is asymptomatic, they will be monitored at the PET center until their blood pressure returns to a normal level.
- B) If the subject has minor symptoms, such as slight nausea or dizziness, they will receive IV fluids to increase their blood pressure. If this does not work, they will be referred to the emergency department at Yale New Haven Hospital.
- C) If the subject has severe symptoms such as vomiting and fainting, they will be referred to the emergency department at Yale New Haven Hospital.

*Safety Visits:*

- 48 hours after the administration of the endotoxin there will be a phone screening using CAM to check for delirium. If there is ongoing delirium then the subject will be directed to immediately go to the emergency room for evaluations and then a follow-up visit can be scheduled with the study doctor
- One week visit: RAVLT, Trail A/B, digit symbol, CAM, ADCS-ADL, MMSE/MOCA, Stroop. 1- 1.5 hrs.

*Optional additional visit for CSF draw*

In volunteers who agree to do so, one 20mls of CSF Sample 0-7days after LPS will be taken at Hospital research unit (HRU) of Yale new haven hospital and banked at [name] in [name] Laboratory. The samples will only be stored in [name] laboratory; they will not be added to one of [name] existing repositories. The samples will be used by only the investigators on this project; they will not be made available to outside researchers.

*Optional additional visits to assess Cognitive Measures with Cog-state Ipad testing*

We may obtain these measures at baseline during the week before LPS injection and the following one during the week after LPS injection. These patients will be separately consented and we will not exclude anyone if they do not accept to do these tasks.

1. Cogstate Battery (30 minutes) – This computerized test battery will assess memory and cognition. The tasks may include:
  - a. International Shopping List Task – a computerized task to assess verbal learning and memory.
  - b. Groton Maze Learning Task – a computerized task to assess executive function and spatial problem solving.
  - c. Detection Task – a computerized task to assess psychomotor function and speed of processing.
  - d. Identification Task – a computerized task to assess visual attention and vigilance.
  - e. One Card Learning Task – a computerized task to assess visual learning and memory.
  - f. One Back/Two Back Tasks – computerized tasks to assess attention and working memory

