At the end of the PET scan day, subjects will be assessed (physical and vital signs) by the study physician. Subjects will be discharged when vital signs are within normal limits and when behavioral changes (if any) are found to be not clinically significant by the MD attending to the subject at the PET Center. If subjects experience any adverse events, they will be treated until they become asymptomatic, prior to discharge. In the proposed study and in our ongoing studies, psychiatric patients who are administered a challenge drug may be admitted to an inpatient unit if psychiatric symptoms worsen or become dangerous on the PET scan day. If required the patients will be assessed by [name] in the neurology clinic and may be sent to emergency department, Yale New Haven Hospital, for admission if necessary. All subjects are followed for 1 week (in person the following day and by phone thereafter) following LPS administration or until potential symptoms (self-report and by assessment) resolve.

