**4. Expected adverse effects:**

We divide the adverse effects into expected and unexpected. For expected adverse effects related to LPS, based on the previous studies of human experimental endotoxemia:

- a) Flu-like symptoms: chills, headache, myalgias and arthralgias, nausea and photophobia can seem to peak about one hour after the administration of the LPS. The phenomenon has a lot of inter- individual variation but within an individual it is dose dependent. The incidence of flu-like symptoms below the dose of 2ng/kg is unrecorded in the literature .

- b) CNS-related adverse effects: in young healthy individuals at 0.8 ng/ml of LPS (2 x the dose we are using), there was some effects on memory, with anxiety and depression emotions. At 0.1 ng/ml there was an improvement in memory recall. Also from clinical experience, which cause much higher levels of inflammation, we know that there is at least a theoretical risk of acute delirium. The course of possible CNS effects follows TNF-alpha which peaks 90 minutes after the administration of the LPS.
- c) CVS-related adverse effects: the most common side effect in the healthy population is tachycardia where there is an increment of roughly 20 beat/min. In a previously pre-disposed individual the administration of LPS can theoretically precipitate arrhythmias .
- d) Pulmonary related adverse effects: There is an association between high dose administration of LPS and increases in the respiratory rate and possibly dyspnea .
- e) Liver and gastrointestinal organs: The administration of high dose (4ng/ml) may change the metabolism of other drugs. Liver is also the main site of removal of LPS from the blood stream. We will exclude patients with evidence of liver damage both semiologically and baseline laboratory values. 

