- b) **Based on previous studies of high dose LPS study in healthy older individuals:** There is one experiment which involves elderly patients receiving endotoxin (published in two papers). Nine elderly patients (median 66 years of age, 61-69) were compared to eight young healthy controls. Administering 2ng/kg intravenously of LPS caused an increase in temperature which was not significantly different between the two groups, but the normalization of the temperature was marginally slower in the elderly group compared to controls. For example at 8 hours there was a 0.7 degree difference between the two

groups. There was a greater TNF-alpha increase in the elderly which had a small delay in termination compared to the control group. They also looked at reduction in mean arterial pressure. The reduction peaked in the young (magnitude 10 mm Hg on average) in the third hour after the administration of the LPS. For the elderly the trough of mean arterial pressure (20 mm Hg on average from a larger baseline MAP) was 6 hours after the LPS.

c) **Alzheimer specific adverse events:** the effect endotoxin administration to subjects with Alzheimer's disease is unknown but two theoretical vulnerabilities may be surmised:

- Vulnerability to Delirium- delirium is a subacute neuropsychiatric syndrome characterized by disturbance and fluctuation of attention, changes in the level and content of consciousness, perceptual disturbance, circadian disruption and other cognitive problems. The relationship between inflammation and delirium is related to the high incidence of delirium in patients with inflammatory, often infectious ailments and higher than normal inflammatory markers . Additionally, delirium is more common in patients who are older and have baseline cognitive impairment. Although we do not anticipate 0.4 ng/kg of endotoxin to cause delirium even in this vulnerable population, we will monitor the incidence of delirium in our study (please see under cognitive safety).

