## 7. Plan for surveillance of cognitive adverse effects

Cognitive adverse effects can occur because of the effect of endotoxin administration (see section 5c) and because of disrupting patient's daily routine and fatigue. Imaging studies which are common in Alzheimer's research, and often in more cognitively impaired individuals, often follow more rigorous procedures of testing. We anticipate that the latter is less likely to be a factor in the cognitive adverse effects. For our purposes we classify cognitive adverse effects as acute and chronic. We following the conventional practice of measuring global cognitive changes by monitoring functional status (ADCS-ADL in this case) and multi-domain screening instruments (MOCA in this case).

*7.1 Protocol for the monitoring of acute cognitive changes for a one-time or test-dose administration of agents*

- The patient's study partner has the PI's cell phone whom s/he can contact with any concerns
- If called, then patient screened with CAM over the phone
- If not called, then the patient is screened with CAM after 48 hours
- If intervention is required that will be prioritized
- If not, then depending on the latest possible interval for late effects there is re-screening. Otherwise Stop.
- If there is delirium, then CAM is repeated every 24 hours until resolution AND ADCS- ADL will be performed in a week to gauge the severity of the adverse effects for reporting.
- MOCA will be performed in a week regardless; and weekly using alternative versions until resolution if  $\geq$  2 change in score.

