## SECTION X: RESEARCH ALTERNATIVES AND ECONOMIC CONSIDERATIONS

1. **Alternatives:** What other alternatives are available to the study subjects outside of the research?

The alternative to participation in this research protocol is to not participate. Subjects will be informed that they are free to choose not to participate and, if they do agree to become a subject, they will be free to withdraw from the study at any time during its course. They will also be informed that if they choose not to participate or if they withdraw, it will not adversely affect their relationship with their doctors or the hospital (see attached Consent Form).

2. **Payments for Participation (Economic Considerations):** Describe any payments that will be made to subjects, the amount and schedule of payments, and the conditions for receiving this compensation.

The following payments will be offered to the patients:

Screening 25

Baseline assessments 50

One week follow up 25

50 for MRI

50 for A-line

350 for each [C] PRB 28 scan=700 total

250 for each [C] PiB Scan

Lipopolysaccharide 150

6- month follow up 150

Cogstate testing (before and after LPS) 50

CSF Draw 350

Total: \$1850

3. **Costs for Participation (Economic Considerations):** Clearly describe the subject's costs associated with participation in the research, and the interventions or procedures of the study that will be provided at no cost to subjects.

There will be no costs to subjects related to participation in this research intervention.

4. **In Case of Injury:** This section is required for any research involving more than minimal risk.
- Will medical treatment be available if research-related injury occurs?
  - Where and from whom may treatment be obtained?
  - Are there any limits to the treatment being provided?
  - Who will pay for this treatment?
  - How will the medical treatment be accessed by subjects?

Medical treatment will be offered to the subjects for any physical injuries that they receive as a result of participating in this research. However, the subject or his/her insurance company is responsible for the cost. Federal regulations require that subjects be told that if they are physically injured, no additional financial compensation is available.

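### No delirium instrument is scheduled between LPS and the 48-hour phone screen, so brief or subtle episodes may be missed from the delirium incidence that the plan undertakes to monitor

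*Combined protocol and SAP*

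**What the plan says.** The Data and Safety Monitoring Plan (DSMP), section 5c, says that the effect of endotoxin in Alzheimer's disease is unknown, names delirium as a theoretical vulnerability, and undertakes that "we will monitor the incidence of delirium in our study", pointing to the cognitive safety section.

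The schedule that serves this undertaking is in two places, and they agree. Under Safety Visits in the Research Plan, "48 hours after the administration of the endotoxin there will be a phone screening using CAM to check for delirium"; the next CAM is at the one-week visit. DSMP section 7.1 says that a call from the study partner prompts a CAM by phone, and otherwise: "If not called, then the patient is screened with CAM after 48 hours". A baseline CAM is part of the screening and baseline battery.

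On timing, DSMP section 4 says: "The course of possible CNS effects follows TNF-alpha which peaks 90 minutes after the administration of the LPS". For older subjects given 2 ng/kg, section 5b reports: "There was a greater TNF-alpha increase in the elderly which had a small delay in termination compared to the control group".

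Other checks fall inside the first 48 hours:

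- Endotoxin Administration: a research nurse and a study physician monitor the subject, the physician until 3 hours after dosing, and normal mental status is one condition of discharge.
- Lipopolysaccharide Administration (risk section): psychiatric symptoms are followed up to 360 minutes, and discharge is allowed "when behavioral changes (if any) are found to be not clinically significant by the MD attending to the subject".
- The same section: "All subjects are followed for 1 week (in person the following day and by phone thereafter".

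**The concern.** An incidence count is only as complete as the looking behind it. The protocol places the likely peak of CNS effects on the LPS day, yet its one named delirium instrument is first scheduled two days later. In between, detection rests on clinical impression and on a lay study partner choosing to phone. A caregiver is an inclusion criterion for the AD group only.

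That combination should serve for obvious delirium. It is weaker for a subtle or short episode, above all in subjects who are already impaired, where acute change is hard to see without comparison with the baseline CAM. DSMP section 5c itself describes delirium as fluctuating.

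At stake is the completeness of the delirium count. The safety committee reviews safety data every 4 months or after every 4 patients, and Pitfalls and Limitations says that this study supplies preliminary data for a larger project.

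**Working it through.** The plan states no figure to reproduce. The check sets the schedule against the expected time course and then sizes the consequence.

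**1. Checks in the first 48 hours**

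| Time after LPS | What is done | Delirium instrument named? |
|---|---|---|
| 0–3 h | Nurse and physician monitoring | No |
| 0–6 h | Sickness and psychiatric symptom checks | No |
| Discharge | Mental status and behavioral change judged clinically | No |
| Next day | In-person contact (risk section only) | No |
| Any time | Study partner may phone | CAM, only if a call is made |
| 48 h | Phone screen | CAM |

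Scheduled CAMs before 48 hours: 0.

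**2. Intervals to the first scheduled CAM**

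- From the expected CNS peak (90 min = 1.5 h, DSMP section 4): 48 − 1.5 = 46.5 h.
- From the end of symptom checks (360 min = 6 h): 48 − 6 = 42 h.

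The second interval is the fairer one, because the first includes the most closely observed hours of the study. Even the 42 hours contain the next-day contact, if it is held.

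**3. Illustration: would an episode still be present at a later CAM?**

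The documents give no durations. Assume an exponential duration with mean d and a CAM that registers only current delirium. Then P(still present at time t) = exp(−(t − onset)/d). With onset at 1.5 h:

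| Mean duration d | At 24 h: exp(−22.5/d) | At 48 h: exp(−46.5/d) |
|---|---|---|
| 6 h | 2.4% | 0.04% |
| 12 h | 15.3% | 2.1% |
| 24 h | 39.2% | 14.4% |
| 48 h | 62.6% | 38.0% |

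With onset at 12 h, the 48-hour column becomes exp(−36/d): 0.25%, 5.0%, 22.3% and 47.2%. For short episodes even a 24-hour CAM misses most, so the pre-discharge CAM and an explicit look-back matter more than an extra time point. The second assumption is pessimistic: a CAM taken with an informant who is asked about the whole interval could register a resolved episode.

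**4. What one missed episode does to the count**

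Using the target of 7 successfully scanned AD subjects and exact (Clopper–Pearson) 95% intervals:

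- 1/7 = 14.3%, interval 0.4% to 57.9%.
- 0/7 = 0%, upper limit 1 − 0.025^(1/7) = 41.0%.

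The intervals overlap widely. The practical change is from one event seen to none seen.

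**5. What is not affected**

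The primary outcome is parietal MARI, and the secondary analyses concern aging, amyloid and cognition; none uses delirium. Stopping criterion x needs a grade 3 cognitive effect beyond one week, or two grade 2 effects persisting after a week, so an episode that clears before 48 hours would not meet it.

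**The case against.** The strongest reply is that the window is far from unobserved, and most of it stands. The hours around the expected peak have a nurse and a physician present, and the section on minimizing risks lists two trained professionals continuously. Flu-like effects at 2 to 4 ng/kg are said to clear within 6 to 8 hours, and the protocol does not anticipate delirium at 0.4 ng/kg. Adverse events are monitored in every subject by any route, and incidence is not defined as CAM positives alone. What survives is narrow: delirium subtle enough to escape staff and study partner, or arising after discharge, and brief enough to clear by 48 hours.

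A reader might infer more than the documents support in four ways:

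- *That the 48-hour CAM is built to miss resolved episodes*, because Safety Visits speaks of ongoing delirium. That word governs referral to the emergency room. The look-back of the phone CAM is simply not stated.
- *That the next-day contact will not take place*, because it is absent from Safety Visits, DSMP section 7.1 and the payments in Section X, which list "One week follow up 25" and nothing earlier after dosing. The payment list is weak evidence: the 48-hour call is not on it either. The mismatch shows only that the two follow-up descriptions need reconciling.
- *That 46.5 hours pass without surveillance.* They pass without a scheduled CAM.
- *That this also undermines grading by daily dependence level* in DSMP section 8.1. That grade is scored from the ADCS-ADL. It is a separate matter, which extra CAMs would not resolve.

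**Conclusion.** The point holds as a minor, inexpensive improvement. The plan undertakes to monitor delirium incidence but, absent a call from the study partner, schedules no structured delirium assessment until 48 hours after LPS. Overt delirium should be caught by the existing observation. Brief or subtle episodes may go uncounted, and the documents give no basis for saying how often.

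The factual part rests on the schedule alone. The persistence figures rest on assumed durations and on a CAM without look-back, so they show direction and not expected loss. With 7 AD subjects the incidence will be imprecise however well it is ascertained; the gain is a more dependable record of whether any episode occurred.

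**What to change.** 1. Give a CAM before discharge on the LPS day, rated over the whole period since dosing, using staff observations and compared with the baseline CAM.
2. Have the 48-hour CAM ask the subject, and the study partner, about delirium that arose and resolved since LPS.
3. Add a CAM at the next-day contact if it is held, or otherwise by phone at about 24 hours. State that the study physician reviews a positive before the emergency-room direction in Safety Visits applies, and say whether the 24-hourly repeats in DSMP section 7.1 start at once or after that review.
4. Make the follow-up text under Lipopolysaccharide Administration agree with Safety Visits and DSMP section 7.1.
5. Count incidence from all these sources, and record the likely cause of each positive (LPS, fatigue or disrupted routine).

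If daily dependence-level grading is to be supported as well, add a brief ADCS-ADL informant question at the same contacts.

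The cost is two short CAMs per subject, one by staff already present and one at an existing contact or by phone, and a small amendment. It adds a few minutes to a long scan day. Some false positives will follow, since DSMP section 7 recognizes that fatigue and disrupted routine can cause cognitive effects; physician review and recording the cause limit this but do not remove it.
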